2. To assess the safety of extending the interval of INR follow-up in patients.

Hypothesis: We hypothesize that there will not be a difference between the bleeding and thromboembolic events from baseline (12 months prior to study enrollment) to events/year at 6, 12, and 24 months.

Hypothesis: We hypothesize that there will not be a difference in the patient's time in therapeutic range (TTR) from baseline (12 months prior to study enrollment) compared to the TTR at 12 and 24 months.

3. To examine patients' and providers' acceptance of the intervention (to extend the follow-up interval of INR monitoring).

Hypothesis: We hypothesize that both patients and providers will favorably view the intervention.

Background:

Anticoagulation treatment with vitamin K antagonists, such as warfarin, can be complicated by many variables, such as drug interactions, diet, health status, other medications, and adherence. Frequent INR monitoring is required to keep patients' INR values within their target therapeutic range to lower the risk of hemorrhagic or thrombotic adverse events. However, some patients remain on the same warfarin dose with INRs within their goal range for extended periods of time. Predictors of very stable INR control for patients on long-term anticoagulation with warfarin include age greater than 70 years, male gender, INR target less than 3.0, and absence of heart failure, diabetes, or other chronic diseases.^{1, 2}

The most recent American College of Chest Physicians 2012 guidelines recommend an INR testing frequency of up to 12 weeks over 4 weeks in patients on warfarin with consistently stable INRs (Grade 2B; weak recommendation, moderate-quality evidence).³ The guidelines define stable INRs as at least 3 months of INRs that are within therapeutic range, thus not requiring changes in warfarin dose. These guidelines are now more comparable to those from the United Kingdom, where the practice of a 12-week INR monitoring interval has been usual practice.⁴ Despite the guideline recommendations, many United States anticoagulation providers are hesitant to extend the duration of INR follow-up to 12 weeks, as historically, the recommended interval and standard clinical practice for INR follow-up was a maximum of 4-6 weeks.

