Patient satisfaction: Study participants will receive a survey at baseline and at approximately 6, 12, and 24 months. The survey includes the Duke Anticoagulation Satisfaction Scale, a validated survey instrument assessing a participant's satisfaction with their anticoagulation therapy and management.¹³ If the participant has a face-to-face visit, they will fill out a paper copy of this survey during a clinic visit. If the participant has a telephone visit, the survey will be mentioned during the phone call and the participant will be mailed a copy of the survey with a pre-addressed stamped envelope. If the participant has a secure messaging visit, the survey will be mentioned in the return secure message and the participant will be mailed a copy of the survey with a pre-addressed stamped envelope. If the survey is not received by study staff within 2 weeks of the visit, the participant will be called to remind them to mail in the survey. Participants will be called up to three times to remind them to mail in the survey. At the end of the study, 10 randomly chosen participants will be asked if they would be interested in attending a focus group to explore their opinions further.

Provider satisfaction, confidence, and knowledge: Pharmacist providers who are study team members will be surveyed prior to the enrollment of the first participant about their knowledge of and confidence with the extended interval protocol. At the end of the study, all pharmacist

providers who are study staff will be invited to attend a focus group to discuss the feasibility of incorporating extended INR intervals into the anticoagulation clinic as well as their satisfaction and attitudes.

Quality assurance: A member of the study staff not involved with the participant's direct warfarin management will conduct a chart review. The chart review will be conducted to evaluate inadvertent protocol violations by anticoagulation study staff in the management of the study participants. Deviations will be categorized and quantified by type and frequency of protocol violation.

Safety: If at any time a participant reports or clinic staff are alerted to a bleeding event, it will be documented in the participant chart, as per standard of care practice. The following criteria, which are currently used in the Anticoagulation Clinic at the Madison VA to collect bleeding and thromboembolic events, will be used to differentiate major and serious bleeding:

Major

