- Fatal or symptomatic bleed into a critical area or organ
- Bleeding leading to hospitalization
- Transfusion of 2 units or more packed red blood cells

Serious

- Bleeding leading to ED or UC visit or additional testing

After a major bleed, the participant will be removed from the extended follow-up interval and will not be eligible to qualify for the extended follow-up interval for 6 months after the event. After a serious bleed, the patient will be managed with usual care. If they did not have a permanent weekly dose change or if the temporary dose change was less than or equal to one month in duration, they must have 2 therapeutic INRs 4 weeks apart to begin the extended INR interval protocol.

If at any time a participant reports or clinic staff are alerted to a thromboembolic event, it will be documented in the EMR. The participant will be removed from the extended follow-up interval and not be eligible to qualify for the extended follow-up interval for 6 months after the event.

If at any time, anticoagulation clinic study staff do not feel it is appropriate to continue a participant with an extended follow-up interval, the participant can return to usual care. If at any time, the participant does not want to continue with an extended follow-up interval, they can return to usual care.

A participant will no longer be eligible for an extended INR interval if they meet any of the exclusion criteria at any time during the study, except for a bleeding or thromboembolic event. If a major bleeding or thromboembolic event occurs, they will be eligible to requalify after being on a stable warfarin dose for 6 months. A patient will also no longer be eligible for the extended INR interval if their INR goal changes and is no longer 2-3. A participant will be withdrawn from the study and no more data collected from the participant if they withdrawal their consent for the study or if death occurs.

A data monitoring committee will review the data collected, including bleeding and thromboembolic events for safety, protocol violations, and feasibility data at six months after the last patient is enrolled (at 3 months or when the 75th patient is enrolled), and then annually. If the data monitoring committee feels that the study is safe to continue, the study will continue until patients have been enrolled in the study for 2 years.

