Adverse events (AEs) collected for this study only include bleeding and thromboembolic events. Serious adverse events (SAEs) will be documented per VA and IRB definitions. AEs will be entered into OnCore after the retrospective review of the medical record at 6, 12, and 24 months after participant enrollment in the study. SAEs are entered into the SAE documentation area in OnCore as they occur, which may not align with the time period for the chart review. The SAEs that include bleeding or thromboembolism will be entered in real-time to the AE table in OnCore.

Measures: The outcomes of this study include feasibility, safety, and acceptability of extending the interval of INR follow-up to 12 weeks in stable warfarin patients. We propose to use the following measures:

1. Feasibility: We will examine the following:
 - a. Rates of participant accrual (patient interest in participating and reasons for not participating). Number of withdrawals and reasons for withdrawal from protocol or study.
 - b. Change in frequency of appointments from baseline
 - c. Frequency and type of protocol deviations from both participants and study staff
 - d. Frequency of time outside of extended INR interval protocol and why
 - e. Knowledge assessment of study staff regarding study protocol
2. Safety: We will examine the following:
 - a. Participant reported and EMR review of bleeding events. Study participant bleeding events for 12 months prior to enrollment and during the study will be compared to the clinic's bleeding event rate. The following definitions will be used to categorize bleeding:
 - i. Major
 1. Fatal or symptomatic bleed into a critical area or organ
 2. Bleeding leading to hospitalization
 3. Transfusion of 2 units or more PRBCs
 - ii. Serious
 1. Bleeding leading to ED or UC visit or additional testing
 - b. Participant reported and EMR review of thromboembolic events that are objectively verified. Study participant thromboembolic events for 12 months prior to study enrollment and during the study will be compared to the clinic's thromboembolic event rate.
 - c. Participant reported and EMR review of healthcare utilization: hospitalizations, ED visits, urgent office visits, telephone triage related to anticoagulation. Utilization for 12 months prior to study enrollment will be compared to utilization during study enrollment.
 - d. Baseline TTR (12 months prior and 6 months prior) for each patient and during study¹⁴
 - e. Number of extreme INRs (<1.5, ≥4.5)

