Sample Size: As this is a feasibility study, the primary concerns are whether or not this process could be incorporated into the normal anticoagulation clinic procedures and workflow. Results from this study can be utilized for calculating sample size and power statistical tests in future larger studies.

Analysis:

Accrual rate will be determined by average participants enrolled per week. Dropout rate will be determined by the number of participants lost to follow up out of the total number of participants

enrolled. Descriptive statistics (percentages, means, rates, and standard deviations) will be determined for all recorded baseline variables. Differences from baseline and at study completion will be compared utilizing McNemar Test for categorical data and paired t-test or Wilcoxon Signed-Rank Test for continuous and ordinal data (respectively). Thematic analysis will be utilized for to determine themes of satisfaction and/or concerns and barriers regarding the extended follow-up protocol from of the focus groups.

References

4. Guidelines on oral anticoagulation: third edition. *Br J Haematol*. May 1998;101(2):374-387.

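### The only named test compares baseline with study completion, so the 6- and 12-month event hypotheses, the 12-month TTR hypothesis and the 6- and 12-month surveys have no planned analysis

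*Combined protocol and SAP*

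**What the plan says.** Three parts of the combined protocol and SAP bear on this.

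- **Specific Aims.** Aim 2 compares the year before enrolment with "events/year at 6, 12, and 24 months" for bleeding and thromboembolism. For TTR, the baseline value is "compared to the TTR at 12 and 24 months". Aim 3 attaches no time to its hypothesis: "We hypothesize that both patients and providers will favorably view the intervention".
- **Procedures and Measures.** Under Patient satisfaction, "Study participants will receive a survey at baseline and at approximately 6, 12, and 24 months". Adverse events are entered after chart review at 6, 12 and 24 months. The TTR measure is "Baseline TTR (12 months prior and 6 months prior) for each patient and during study", by the Rosendaal method, with no on-study window given. Measures also sets participants' events against the clinic's rate and compares healthcare use before and during enrolment, without naming a test there.
- **Analysis.** "Differences from baseline and at study completion will be compared utilizing McNemar Test for categorical data and paired t-test", with a Wilcoxon signed-rank alternative. Descriptive statistics are promised for baseline variables only. A dropout rate is defined, but there is no analysis set and no rule for missing values.

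Under Safety, subject to the data monitoring committee's agreement, "the study will continue until patients have been enrolled in the study for 2 years". I therefore read study completion as 24 months.

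**The concern.** The aims and the data schedule follow participants through several time points, while the analysis goes straight from the first to the last. Someone following the Analysis section as written would have no stated way to answer two of the three event questions or one of the two TTR questions in Aim 2, and nothing to do with the 6- and 12-month surveys.

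The second part concerns satisfaction. A paired test needs both values. A participant who returns the baseline, 6- and 12-month surveys but not the last one contributes nothing to the only named test. People who stop returning surveys may well be those whose opinion of the longer interval has worsened. Losing them would move the result towards the favourable view that Aim 3 predicts.

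**Working it through.** **1. Time points against the named test**

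| Outcome | Follow-up times in the aims or schedule | Reached by the named test | No analysis stated |
|---|---|---|---|
| Bleeding and thromboembolic events | 6, 12, 24 months (Aim 2) | 24 | 6, 12 |
| TTR | 12, 24 months (Aim 2) | 24 | 12 |
| Satisfaction survey | 6, 12, 24 months (schedule; Aim 3 gives no time) | 24 | 6, 12 |

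There is no 6-month TTR hypothesis, so none is missing. The plan gives no alpha, power, SD or effect size, so there is no stated figure to reproduce.

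**2. Size of a completers-only effect on satisfaction**

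Let m be the share without a 24-month survey and d the amount by which their mean change from baseline is worse than that of responders, in SDs of the change. Then

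bias in the completers' mean change = m × d.

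The documents give neither input, so both are assumptions:

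| m | Complete pairs of 75 | Bias if d = 0 | Bias if d = 0.5 |
|---|---|---|---|
| 10% | 67 | 0 | 0.05 SD |
| 20% | 60 | 0 | 0.10 SD |
| 30% | 52 | 0 | 0.15 SD |

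For scale, the paired difference detectable with 60 pairs (two-sided 5%, 80% power, also assumed) is (1.960 + 0.842)/√60 = 0.36 SD. What matters is d for the *change*. If non-responders were equally less satisfied at baseline, the difference cancels and the bias is zero.

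**3. TTR**

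TTR is calculated from charted INRs and does not depend on a returned form. Under Safety, data collection ends only on withdrawal of consent or death, and a participant who leaves the extended interval goes back to usual care and stays in the study. TTR can be calculated over whatever follow-up exists. Whether the planned comparison excludes anyone depends on the on-study window, which is not defined.

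**4. Would event tests at 6 and 12 months help?**

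Expected on-study events = 75 × 2013 clinic rate × years:

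- Major bleeding at 1.88%: 0.7, 1.4 and 2.8 by 6, 12 and 24 months.
- Major bleeding, serious bleeding and thromboembolism together, 1.88% + 0.5% + 0.22% = 2.6%: 1.0, 2.0 and 3.9.

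The exact two-sided McNemar p-value when all k discordant pairs go one way is 2 × 0.5^k. It is 0.0625 for k = 5 and 0.031 for k = 6, so at least six are needed, all in one direction. Such tests could hardly ever reject.

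An interval says more. With no events, the exact 97.5% upper limit is 3.689 divided by person-years. With all 75 followed (37.5, 75 and 150 person-years), that is 9.8, 4.9 and 2.5 per 100 person-years.

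**The case against.** The strongest reply is that the Sample Size section declares a feasibility study whose main question is whether the process fits clinic workflow. No power is claimed, and step 4 shows that extra event tests would tell almost nothing. That stands, and it is why the remedy for events is estimation and not more tests. It does not excuse the mismatch. The same section offers the results as input for sizing larger studies, and visit-specific changes, SDs, correlations and missingness are the inputs needed for that.

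A second reply is that silence is not exclusion. A reader might infer that the intermediate data will be thrown away. The documents do not say so: charts are reviewed at 6, 12 and 24 months, and the data monitoring committee sees events six months after the last enrolment and then annually. The supportable statement is that these data have no planned analysis.

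A third is that up to three reminder calls are planned for late surveys. They should lower the missing share, but there is no rule for surveys that never arrive.

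Finally, a repeated-measures model rests on data missing at random. If people fail to respond because of dissatisfaction at 24 months that their earlier surveys do not show, the model will not remove the bias. That is correct and limits what the fix can promise.

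**Conclusion.** The mismatch holds on the text: events at 6 and 12 months and TTR at 12 months are hypotheses without a stated test, and the 6- and 12-month surveys have no planned analysis. For satisfaction, loss of participants without a 24-month survey follows from a paired test with no missing-data rule, taking study completion as 24 months. The direction and size of any bias depend on assumptions. The 0.1 SD figure needs 20% missing and a change 0.5 SD worse among them.

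Two stronger readings are tempting and should not be carried over:

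- *TTR also rests on completers.* Not established, for the reasons in step 3. The supportable gap is the undefined window.
- *Using all surveys makes the comparison 18% more precise.* With equal correlation ρ between visits, a single change has variance 2σ²(1−ρ), and the average of three follow-up visits minus baseline has (4/3)σ²(1−ρ). The ratio is 2/3 and the SE ratio 0.816. With TTR's two follow-up times the ratio is 3/4. Either gain belongs to an average over visits, which is not what Aim 2 asks. For the 24-month contrast with complete data and an unstructured covariance, the model's SE equals that of the paired test. Any gain comes from participants with incomplete data.

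This is a cheap improvement worth making. It is not a flaw that undermines the study.

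**What to change.** Extend the Analysis section as follows.

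- **Satisfaction (baseline, 6, 12, 24 months).** Fit a linear mixed model for repeated measures with visit as a category and unstructured covariance, using all enrolled participants with any survey. Report each visit against baseline with an interval. Keep the paired t-test or Wilcoxon test as a completers-only sensitivity analysis, and report the number of surveys returned at each visit.
- **TTR.** Define the 12- and 24-month windows, include participants with partial follow-up, and report the change from baseline at both times with intervals.
- **Events.** Report rates per person-year with exact intervals at 6, 12 and 24 months beside the baseline year. Rates put windows of unequal length on one scale.

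The cost is a few sentences and slightly more analysis work, with no new data, visits or participants. The downside is the missing-at-random assumption: the model reduces dropout bias compared with dropping incomplete cases, but does not guarantee its removal.
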